## Study Protocol/Methods

We conducted a randomized clinical trial at a single tertiary care center in central Massachusetts from March 2021 until April 2023. Prior to study initiation, approval was obtained from the University of Massachusetts Chan Medical School institutional review board. Written informed consent was obtained from all participants before enrollment and patient safety data and trial progress was assessed via a Data Safety Monitoring Board with all reporting following Consolidated Standard of Reporting Trials guidelines.

Inclusion criteria included pregnant patients aged 18 years or older with a known diagnosis of T1DM that were managed with CSII/insulin pump. All included participants had to obtain pregnancy and delivery care the study institution and had to be able to provide written informed consent in English or Spanish. Patients were not eligible if they were under the age of 18 years old, had multiple gestations, had altered state of consciousness intrapartum, were critically ill requiring intensive care unit admission, at risk for suicide, presented with diabetic ketoacidosis on admission for delivery, had an intrauterine fetal demise prior to labor, fetal anomalies, or if the participant was unable to partake in their own care.

All eligible participants were approached antenatally during routine prenatal care and consented for participation. Participants were then randomly allocated to either continuation of an intrapartum CSII/insulin pump or intravenous insulin infusion. Permutated block randomization with varying blocks sizes was used to stratify randomization by intrapartum glycemic management strategy (CSII vs. IV). The resulting group allocations were kept in sealed, opaque envelopes until opened by the provider at the time of randomization. Patients and providers were not blinded to randomization given active participation of providers and patients was needed in both study arms. Once admitted for labor, two separate intrapartum glycemic protocols were followed based on randomization category (Supplementary Figures 1 and 2).

All medical records were reviewed for maternal demographics, clinical characteristics, and perinatal outcomes including primary and secondary outcomes. The primary outcome for the study was the first neonatal blood glucose level measured after birth. At our institution, it is policy that all neonates of mothers diagnosed with pre-gestational diabetes receive a heel-stick glucose measurement within the first 2 hours of life. Neonatal hypoglycemia was defined as blood glucose level less than 40 mg/dL, which prompts treatment and further monitoring at our study institution. In order to detect a 10 mg/dL difference in mean neonatal blood glucose levels between groups with a type 1 alpha error of 0.05 and 80% power with equal group sizes, 35 participants in each group were needed for a total sample size of 70 patients.

Secondary neonatal outcomes included mean neonatal glucose in the first 24 hours of life, neonatal hyperglycemia treatments including oral or intravenous treatment, 5 minute APGAR less than 7, NICU admission, neonatal birthweight, neonatal birthweight meeting large for gestational age criteria by Fenton growth calculator for preterm infants or World Health Organization growth calculator for term infants, or additional adverse neonatal outcomes including respiratory distress requiring intubation or continuous positive airway pressure (CPAP), hyperbilirubinemia, and neonatal cooling. Maternal secondary outcomes included intrapartum hypoglycemic events defined as blood glucose less than 60 mg/dL, intrapartum severe maternal hyperglycemic events defined as blood glucose greater than 200 mg/dL, development of diabetic ketoacidosis intrapartum, mode of delivery, shoulder dystocia at delivery, development of gestational hypertension or pre-eclampsia, maternal blood transfusion, and maternal intensive care unit admission.

All summary data were collected and managed using REDCap tools hosted at UMASS Chan Medical School. Summary data are reported as frequencies for categorical variables and

mean (standard deviation) or median (interquartile range) for continuous variables. All categorical variables were compared using Fisher exact test and Chi square testing where appropriate, while continuous variables were assessed for normality and t-tests or Wilcoxon rank sum tests were used where appropriate. For all analyses, a two-sided significance level of  $P<0.05$  was considered statistically significant. Analyses were performed using STATA/SE 17.0 (StataCorp, College Station, TX).

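### Does stratifying randomisation by the treatment arm itself (CSII vs. IV) leave the primary analysis mismatched to the design?

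*Combined protocol and SAP*

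**What the plan says.** The combined protocol and SAP has one heading, Study Protocol/Methods. Four parts of it bear on this point.

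- **Randomisation.** Participants were "randomly allocated to either continuation of an intrapartum CSII/insulin pump or intravenous insulin infusion". The next sentence says that permuted-block randomisation with varying block sizes "was used to stratify randomization by intrapartum glycemic management strategy (CSII vs. IV"). Assignments were held in sealed, opaque envelopes, and the intrapartum glucose protocol then followed from the assignment.
- **Eligibility and setting.** Participants were pregnant patients "with a known diagnosis of T1DM that were managed with CSII/insulin pump". The trial ran "at a single tertiary care center in central Massachusetts from March 2021 until April 2023".
- **Sample size.** For a 10 mg/dL difference in the first neonatal glucose, with alpha 0.05 and 80% power, "35 participants in each group were needed for a total sample size of 70 patients". No standard deviation and no stratum appear in the calculation.
- **Analysis.** "continuous variables were assessed for normality and t-tests or Wilcoxon rank sum tests were used where appropriate". These are two-group comparisons with no stratum term, at a two-sided 5% level.

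**The concern.** A stratification factor must be known before allocation and must differ between participants. The factor named here does neither. It is the assigned treatment, which exists only once the envelope is opened. Taken literally, the stratification described could not have been carried out.

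That leaves two possible accounts. Either (a) the trial used plain permuted blocks and described them badly, or (b) it stratified on a real baseline factor that the text fails to name. The difference could affect the primary analysis. Under (a), the unadjusted test matches the design. Under (b), stratification forces the factor to balance between arms, but the unadjusted standard error still includes the variation due to that factor. If the factor predicts neonatal glucose, the test is then too cautious and loses power. In a trial of 70 participants, that would be worth knowing.

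**Working it through.** **1. Which reading does the text support?** Each candidate for a real stratum is set against the document.

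| Candidate | What Study Protocol/Methods says | Possible stratum? |
|---|---|---|
| Intrapartum strategy, CSII vs. IV | Identical to the two randomised arms, and set by the assignment | No, known only after allocation |
| Insulin delivery at entry | "known diagnosis of T1DM that were managed with CSII/insulin pump" is an entry requirement | No, it does not vary |
| Centre | One centre | No, it does not vary |
| Any other baseline factor | None named under randomisation, sample size or analysis | No textual support |

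The sentence does not leave a blank where a factor should be; it fills the place with the two arms. If the verb is read as *allocate*, the sentence makes sense: permuted blocks of varying size assigned participants to CSII or IV. The sample-size and analysis paragraphs, neither of which has a stratum, agree with that reading.

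**2. The plan's own figure.** The 35 per group cannot be reproduced directly, because no SD is given. Solving backwards with the normal approximation:

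SD = 10 / [(1.960 + 0.842) × √(2/35)] = 10 / (2.802 × 0.2390) ≈ 14.9 mg/dL.

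The noncentral t gives 14.72 mg/dL. No stratum enters the formula, so correcting the sentence leaves the sample size at 70.

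**3. Type I error under (a), unstratified blocks.** The check was a simulation of 20,000 trials per setting. Assumptions: blocks of 4 and 6, and one prognostic factor correlated r with the outcome. The unadjusted t-test rejected in 5.1%, 5.0% and 5.0% of null trials at r = 0.2, 0.4 and 0.6. The nominal level holds. Chance imbalance in a prognostic factor is already covered by the standard error.

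**4. Type I error under (b), a hypothetical stratifier.** Assume one balanced binary factor with correlation r. Stratified blocking reduces the true variance of the difference by the factor (1 − r²), while the t-test still uses the full variance. The actual two-sided error is therefore about 2 × P(Z > 1.96/√(1 − r²)). For such a factor the gap between the two stratum means is 2 × r × SD, with SD = 14.72 (the back-solved assumption).

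| r (assumed) | 1.96/√(1 − r²) | Type I error, formula | Simulated (40,000 runs) | Gap between strata, mg/dL |
|---|---|---|---|---|
| 0.2 | 2.00 | 4.5% | 4.4% | 5.9 |
| 0.4 | 2.14 | 3.2% | 3.4% | 11.8 |
| 0.6 | 2.45 | 1.4% | 1.5% | 17.7 |

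Every figure lies below 5%, so no risk of extra false positives appears. The two larger departures need a factor that shifts neonatal glucose by more than the 10 mg/dL the trial was sized to detect. These figures are for the t-test; the Wilcoxon option was not simulated.

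**The case for a change.** The strongest case for a change runs as follows. The statement is false as written. The document commits the trial to the CONSORT reporting guidelines, which makes an accurate account of randomisation its own standard. The text cannot strictly rule out an unnamed stratifier. Looking at the randomisation list and correcting one sentence costs almost nothing. One could go further and ask for a linear model adjusted for a baseline glycaemic measure, since no prognostic factor is handled anywhere.

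The first part stands: the wording is wrong, and anyone preparing the report can put it right from the list, confirming the allocation ratio at the same time. But that is copy-editing. It alters no procedure, test or sample size. That the text does not exclude a hidden stratifier is not evidence for one, and the error figures under that reading rest on an invented factor and an invented correlation. Should the list show that a baseline factor was used, naming it and including it in the model would be routine practice.

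The adjusted model is a separate preference and does not repair the sentence. With an assumed SD of 14.72 and r = 0.4, the standard error would fall from 14.72 × √(2/35) = 3.52 to 3.52 × √0.84 × √(1 + 1/66) = 3.25, a modest gain of about 8%. The document says only that "All medical records were reviewed for maternal demographics, clinical characteristics, and perinatal outcomes", and it names no glycaemic measure taken before randomisation. Because the trial ran from March 2021 to April 2023, a covariate chosen now would probably be post hoc.

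**Conclusion.** The sentence misuses the word *stratify*, and no change to the plan follows. On the only reading the document supports, allocation was by unstratified permuted blocks of varying size. The unadjusted comparison then matches the design and the t-test holds its 5% level. The planned 35 per group and the interpretation of the primary outcome are unaffected. Random allocation, varying block sizes and sealed opaque envelopes are all still described, and nothing here points to biased allocation.

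The conclusion rests on one assumption: that the randomisation list contains no baseline stratum. If that were wrong, the planned t-test would be conservative, by about half a percentage point at an assumed r of 0.2 and by more only for a factor with a larger effect on neonatal glucose. It would not produce excess false positives.

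### Does the claim of 80% power with 35 per group fail because the SD is unstated and nothing is allowed for loss or crossover?

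*Combined protocol and SAP*

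**What the plan says.** All the relevant text stands under Study Protocol/Methods in the combined protocol and SAP.

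- **Sample size.** The target is a difference of 10 mg/dL in the group means of neonatal glucose, alpha is set at 0.05, and the result reads "80% power with equal group sizes, 35 participants in each group were needed for a total sample size of 70 patients". The sentence names no SD, no source for one, and no inflation for loss or crossover.
- **Eligibility and allocation.** Participants consent during prenatal care and are then randomised; the two glycaemic protocols begin at admission for labour. The ineligible include patients who "presented with diabetic ketoacidosis on admission for delivery, had an intrauterine fetal demise prior to labor". Pregnancy and delivery care must take place at the study institution.
- **Primary outcome.** This is the first neonatal glucose. By institutional policy every neonate of a mother with pre-gestational diabetes has a heel-stick within two hours of birth.
- **Analysis.** Continuous variables are checked for normality, after which "t-tests or Wilcoxon rank sum tests were used where appropriate". The test is two-sided: "For all analyses, a two-sided significance level of" 0.05 applies. No analysis population is named.

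**The concern.** A difference in means, an alpha and a power do not fix a sample size; an SD is also needed. Without it a reader cannot tell whether 35 per group came from local data, from a convenient round value or from the number of patients available.

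Several features of the design could also lower power below the stated figure. Allocation appears to precede labour, yet some exclusions can be known only at or after admission, so some randomised participants might not be analysed. The trial is open label and the insulin route could change during labour, which would dilute the contrast. A rank-sum test, if applied to normal data, is slightly less efficient than the t-test.

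What is at stake is how a non-significant result is read. If the real power were nearer 55% than 80%, such a result would say little about whether a 10 mg/dL difference exists.

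**Working it through.** **Inputs from the documents.** Difference 10 mg/dL; two-sided alpha 0.05; power 80%; n = 35 per group. The SD is not given, so the stated size can be checked only by solving for it.

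**Implied SD, normal approximation.** From n = 2(1.960 + 0.8416)² × SD²/10²,

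SD = 10 × √(35/2) / 2.8016 = 41.83 / 2.8016 = 14.93 mg/dL.

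**Implied SD, t-test.** Power is the probability that a noncentral t variable with 68 degrees of freedom and noncentrality 10 / (SD × √(2/35)) falls beyond ±1.995. This equals 0.80 at SD = 14.72 mg/dL.

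**Which SDs return 35?** Those from 14.50 to 14.72 (t-test) and from 14.72 to 14.93 (normal approximation). A planning SD of 15 gives 2 × 2.8016² × 2.25 = 35.3, so 36 per group, or 37 by the t-test. The stated size is within two per group of that round value.

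**Power for 10 mg/dL at 35 per group, by SD.** All these SDs are assumed.

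| SD (mg/dL) | Power (t-test) |
|---|---|
| 12 | 93% |
| 13 | 89% |
| 14 | 84% |
| 14.7 | 80% |
| 15 | 78.5% |
| 16 | 73% |
| 18 | 63% |
| 20 | 54% |
| 25 | 38% |

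A table starting at 15 would show only shortfalls. Nothing in the documents favours that half of the range over the other.

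**Loss and dilution.** Loss reduces n. Change of route is modelled as the 10 mg/dL difference multiplied by (1 − p). Both rates are assumed.

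| Scenario | SD 14.7 | SD 13 |
|---|---|---|
| 33 analysed per group | 77.7% | 86.8% |
| 31 analysed per group | 75.0% | 84.6% |
| 30 analysed per group | 73.6% | 83.4% |
| 10% dilution (difference 9) | 71.4% | 81.5% |
| 20% dilution (difference 8) | 61.2% | 71.8% |

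Complete data and full adherence are thus needed for 80% only if the SD is at its limit. At SD 14, 32 per group already suffice, so three losses per group can be absorbed.

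**Rank-sum test.** Its asymptotic efficiency on normal data is about 0.955, which makes 35 per group equivalent to 35 × 0.955 = 33.4. Power at SD 14.7 then falls from 80% to about 78%. The plan uses this test where appropriate after a normality check, that is, for non-normal data, where it can be the more efficient of the two.

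**The case for a change.** The strongest case for acting is that an unstated SD makes the calculation uncheckable and that the remedy is cheap: a sentence giving the SD and its source, and the mean difference reported with its 95% confidence interval. The interval's half-width would be about 7.0 mg/dL at SD 14.7 (1.995 × 14.7 × √(2/35)) and 9.5 at SD 20. The analysis text mentions P values and no interval, so a null result could be taken for equivalence of the two routes.

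The first part stands: the SD, its source and any allowance are missing, and at the implied SD there is no margin. The rest is weaker.

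- The eligibility paragraph lists who was not eligible. It contains no rule for removing anyone after randomisation, so loss by that path is possible but not planned.
- The outcome is a routine in-hospital measurement within two hours of birth, in patients who must deliver at the study site. The usual losses to follow-up are largely absent.
- No text gives a crossover rate. The supplementary figures holding the intrapartum protocols are not shown, so nothing can be inferred from their absence.
- The plan nowhere says that a non-significant result will be read as no difference, and it commits to CONSORT reporting. Advice on intervals is sound but generic; it does not correct anything the plan states.

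**Conclusion.** No change to the plan follows. The size of 35 per group is reproduced by an SD of about 14.5 to 14.9 mg/dL and lies within two per group of the answer for a round SD of 15, so no arithmetic error is shown. What is missing is one reported input and a statement that the 80% refers to 35 analysed per group. An analyst can recover the first by the back-calculation above and will read the second in the ordinary way.

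If the true SD is near 14.7, a loss of four per group costs about five percentage points of power. If it is 20, power is 54%; if it is 13, the same loss leaves 85%. These SDs and loss rates are assumptions, and the documents do not help to choose among them. The methods text describes a trial run from March 2021 to April 2023, so restating the planning power would alter neither the design nor the data. The precision achieved will depend on the observed SD and the numbers analysed.

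### Birthweight and large-for-gestational-age status are tested as outcomes of insulin protocols that start only at admission for labour, and the hypertensive outcome has no onset window

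*Combined protocol and SAP*

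**What the plan says.** All the relevant text is under Study Protocol/Methods in the combined protocol and SAP.

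- **Start of treatment.** "Once admitted for labor, two separate intrapartum glycemic protocols were followed based on randomization category". The arms are defined by how insulin is given during labour.
- **Consent and allocation.** "All eligible participants were approached antenatally during routine prenatal care and consented for participation". Allocation comes next: "Participants were then randomly allocated to either continuation of an intrapartum CSII/insulin pump or intravenous insulin infusion". Neither the gestational age at randomisation nor the interval from randomisation to labour is given.
- **Blinding.** "Patients and providers were not blinded to randomization".
- **Neonatal secondary outcomes.** The list includes "neonatal birthweight, neonatal birthweight meeting large for gestational age criteria".
- **Maternal secondary outcomes.** The list includes "development of gestational hypertension or pre-eclampsia", with no limit on when the disease began. In the same list, maternal hypoglycaemia and severe hyperglycaemia are limited to labour, and so is ketoacidosis: "development of diabetic ketoacidosis intrapartum".
- **Tests.** "All categorical variables were compared using Fisher exact test and Chi square testing where appropriate". Continuous variables get a t-test or rank sum test. One two-sided 5% threshold covers all analyses. Nothing marks birthweight, LGA or hypertensive disease as descriptive.

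**The concern.** A between-arm test of a secondary outcome is normally read as evidence about the treatment. That reading needs the treatment to be able to change the variable. Insulin delivery that starts at admission for labour has no plausible route to birthweight, or to LGA status, which is derived from birthweight and gestational age. It also cannot have caused hypertensive disease that was already present at admission.

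Listed and tested beside outcomes that the protocols could affect, such as the neonatal glucose measures, these variables invite the same interpretation. A P value below 0.05 for birthweight would stand in the results as a difference between pump and intravenous insulin when it says nothing about either. For hypertensive disease, cases that precede treatment are mixed with any that follow it, so the comparison does not isolate what the protocols could have influenced.

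**Working it through.** **1. Timing, variable by variable**

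| Variable | Limited to labour in the plan? | Can the assigned protocol change it? |
|---|---|---|
| Maternal hypoglycaemia, severe hyperglycaemia, ketoacidosis | Yes | Yes |
| Birthweight | No | Not plausibly; fetal weight is essentially set at admission |
| LGA status | No | Not plausibly; derived from birthweight and gestational age |
| Gestational hypertension or pre-eclampsia | No | Not if onset precedes the protocol; not excluded if onset follows it |

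That fetal weight is essentially set at admission is a clinical premise; the documents do not state it.

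**2. Share of the outcome list**

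Counting the items gives 9 neonatal and 8 maternal secondary outcomes, 17 in all. Two (birthweight and LGA) are clearly affected. A third (hypertensive disease) is affected in part.

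**3. Group size used below**

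The plan states 35 per group for a 10 mg/dL difference, 5% two-sided error and 80% power. It gives no standard deviation, so the figure cannot be reproduced from the text alone. Solving n = 2(1.96 + 0.84)² SD² / 10² for n = 35 implies an SD of about 14.9 mg/dL. Only the 35 per arm is used here.

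**4. False-positive risk when treatment can have no effect**

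Randomisation keeps each single test at about 5%.

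If the tests were independent:
- two outcomes: 1 − 0.95² = 9.75%
- three outcomes: 1 − 0.95³ = 14.3%

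Independence cannot hold for the first two, because LGA is computed from birthweight. Simulating 35 against 35 with no treatment effect, 40% LGA (assumed), 30% hypertensive disease (assumed, and independent of the other two) and a correlation of 0.8 to 1.0 between birthweight and the variable underlying LGA (assumed) gives the following, with simulation error of a few tenths of a percentage point:

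| At least one P < 0.05 among | Fisher for binary outcomes | Chi-square for binary outcomes |
|---|---|---|
| Birthweight and LGA | 6.3% to 6.9% | 7.7% to 8.5% |
| Those two plus hypertensive disease | 9.0% to 9.4% | 12.5% to 13.0% |

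A separate simulation with chi-square tests and assumed LGA rates of 30% and 50% gave 8.4% and 7.6% for the pair. The second row treats every hypertensive case as beyond the reach of treatment, so it overstates that outcome's part if some cases begin after the protocol starts.

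**5. Scale**

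If all 17 secondary outcomes were null and independent, the chance of at least one false positive would be 1 − 0.95¹⁷ = 58%. With two removed it is 1 − 0.95¹⁵ = 54%. The case for the change is therefore mainly about interpretation; it does little for multiplicity.

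**The case against.** Four points can fairly be made for the plan.

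**The tests are valid.** Randomisation holds each at its nominal level. This stands. A reader might infer that the plan builds in a false effect; it does not. Nothing in the design creates a difference, and a significant result would most likely be an ordinary type I error.

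**These variables may not be baseline.** Consent was antenatal, allocation followed, and care was open label. If allocation came well before labour, birthweight and hypertensive disease arose after randomisation, and knowledge of the arm could have altered antenatal care or delivery timing, and so birthweight (LGA less so, being relative to gestational age). This also stands as a possibility. The documents neither show that it happened nor exclude it, so one cannot say that a difference could only be chance. It does not rescue the outcomes, though: such a difference would reflect knowing the assignment and not the way insulin was given.

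**Hypertensive disease may begin during or after labour.** The wording allows this, and the documents do not say how many cases start earlier. So the outcome should be given an onset window and not be removed.

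**No text says that a difference would be attributed to insulin.** True; the plan lists outcomes and tests without an interpretation rule. But it tests these variables exactly as it tests the others and nowhere marks them as descriptive.

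**Conclusion.** The point holds and is minor. Two of the 17 secondary outcomes, birthweight and LGA, are tested although the assigned protocols cannot plausibly change them. A third, hypertensive disease, admits cases that precede treatment because it has no onset window. The chance of at least one spurious significant result is roughly 6% to 8% for birthweight and LGA together, and at most about 9% to 13% with hypertensive disease added. These ranges rest on 35 per arm from the plan and on assumed values for the LGA rate, the hypertension rate and the correlation.

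A reader might also infer that the plan loses power by not using birthweight as a covariate for neonatal glucose. The documents give neither a correlation nor a standard deviation from which to judge that, and it is not part of this point. The primary outcome, its test and the sample size are unaffected.

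**What to change.** - Take birthweight and LGA off the list of secondary outcomes. Report them by arm as pre-treatment descriptive variables, without treatment-effect P values. Avoid the label baseline, because randomisation may have preceded them.
- Count gestational hypertension or pre-eclampsia as an outcome only when onset follows the start of the assigned protocol. List earlier onset with the descriptive variables.
- State when randomisation took place relative to admission for labour.

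The text describes the trial in the past tense, so if it is the final record the change belongs in the reporting and should be marked as made afterwards. The cost is a shorter outcome list, two or three rows moved between tables, and abstraction of hypertension onset time. The documents do not mention onset time as a collected variable, but medical records were already reviewed for outcomes. No new patients, and no change to the primary analysis, are needed.

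### The primary comparison is valid but unadjusted; adjusting for one or two maternal covariates fixed before allocation may gain precision at almost no cost

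*Combined protocol and SAP*

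**What the plan says.** Everything relevant is in the combined protocol and SAP, under Study Protocol/Methods.

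- **Outcome.** "The primary outcome for the study was the first neonatal blood glucose level measured after birth". It is a continuous measure.
- **Analysis.** One rule covers all continuous data: "continuous variables were assessed for normality and t-tests or Wilcoxon rank sum tests were used where appropriate". No regression model, covariate or adjusted sensitivity analysis appears anywhere.
- **Data in hand.** "All medical records were reviewed for maternal demographics, clinical characteristics, and perinatal outcomes including primary and secondary outcomes". No individual maternal variable is named, and the text does not say which were recorded before allocation.
- **Randomisation.** Permuted blocks are used, but the only stratification factor named is the treatment itself (pump versus intravenous insulin). No prognostic factor is balanced by design.
- **Size.** The target is a difference of 10 mg/dL, at alpha 0.05 and 80% power. For this the plan states that "35 participants in each group were needed for a total sample size of 70 patients". No standard deviation is given.

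**The concern.** In a trial of 70 women, maternal characteristics that predict neonatal glucose can differ between arms by chance, and whatever they explain stays in the error term of an unadjusted test. The usual remedy is to adjust for a small number of prognostic variables measured before allocation. This plan collects candidate variables but uses none in the treatment comparison, and the randomisation does not balance any of them.

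What is at stake is efficiency: a wider confidence interval and a lower chance of detecting the 10 mg/dL target than the same 70 women might provide.

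**Working it through.** **Inputs from the documents:** difference 10 mg/dL; 35 per arm; alpha 0.05, two-sided; power 80%; unadjusted test.

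**Inputs assumed:** the standard deviation (back-solved below) and the share of outcome variance explained by the covariate, R², taken over 0 to 0.30 because the documents give no figure.

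**1. The plan's own figure.** The 35 per arm cannot be reproduced forwards without an SD, so it is solved backwards.
- Normal approximation: SD = 10 × √(35/2) / (1.960 + 0.842) = 14.9 mg/dL.
- Exact two-sample t-test (noncentral t, 68 df): SD = 14.72 mg/dL gives 80% power.

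The exact value is used from here on.

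**2. Unadjusted comparison.**
- SE = 14.72 × √(2/35) = 14.72 × 0.239 = 3.52 mg/dL.
- 95% CI half-width = 1.995 × 3.52 = 7.02 mg/dL. Power is 80% by construction.

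**3. Adjusted comparison, one covariate.** The residual SD is 14.72 × √(1 − R²). One degree of freedom is lost (67 remain, t = 1.996). Chance imbalance in the covariate inflates the variance on average by 1 + 1/66 = 1.015. So SE = 14.72 × √(1 − R²) × 0.239 × √1.015.

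| R² (assumed) | Residual SD | SE | 95% CI half-width | Power for 10 mg/dL |
|---|---|---|---|---|
| Unadjusted | 14.72 | 3.52 | 7.0 | 80% |
| 0 | 14.72 | 3.55 | 7.1 | 79% |
| 0.04 | 14.42 | 3.47 | 6.9 | 81% |
| 0.10 | 13.96 | 3.36 | 6.7 | 83% |
| 0.20 | 13.17 | 3.17 | 6.3 | 87% |
| 0.30 | 12.32 | 2.97 | 5.9 | 91% |

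The adjusted SE drops below the unadjusted one once (1 − R²) × 1.015 is less than 1, that is, at an R² of about 0.015 (a correlation of about 0.12).

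**4. Validity of the planned test.** In 10,000 simulated trials per setting with no true difference, the unadjusted test rejected in 5.0%, 5.0% and 5.3% at covariate-outcome correlations of 0, 0.3 and 0.5. The adjusted test rejected in 4.8%, 5.0% and 5.0%. Both hold the nominal level.

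**5. Size of chance imbalance.** The standardised difference between arms in a baseline covariate has SD √(2/35) = 0.239.
- At the 95% limit it is 1.96 × 0.239 = 0.47 SD. With correlation 0.3 to 0.5 the unadjusted estimate moves by 0.47 × 0.3 × 14.72 = 2.1 mg/dL to 0.47 × 0.5 × 14.72 = about 3.4 mg/dL.
- At the median it is 0.67 × 0.239 = 0.16 SD, which moves the estimate by 0.7 to 1.2 mg/dL.

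This movement is part of the 3.52 mg/dL SE in step 2. It is the precision loss of step 3 seen from another side, and the two must not be added.

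**The case against.** The strongest reply is that nothing here is an error. A t-test or rank-sum test is a valid analysis of a randomised comparison, and nothing in the documents shows that the trial misses its 80% target. The gain is also unproven: no covariate is named and no correlation is given. Allocation followed antenatal consent, so a variable fixed before it may be remote from labour and predict poorly a heel-stick glucose taken within two hours of birth. At R² = 0.04 the gain is about 1 point of power. Finally, the text is written in the past tense, so making a new model primary could replace the stated analysis after the data are known.

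All of this stands, and it limits the point to a possible efficiency gain. It does not remove the point, because the pay-off is lopsided: under 1 point of power lost if the covariate is useless, against about 3 to 11 points gained if R² is 0.10 to 0.30.

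Two stronger readings are tempting and are not supported.

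- *Chance imbalance biases the result.* Over repeated randomisation it does not, and the unadjusted standard error already covers it. The 2.1 to 3.4 mg/dL shift is the 95% extreme, not the typical case.
- *Maternal characteristics are used only for significance tests between arms.* The plan also reports summary data descriptively. That baseline variables are tested at all is an inference from general wording such as "All categorical variables were compared using Fisher exact test and Chi square testing where appropriate"; it is plausible but not stated. A figure for false-positive baseline differences would need an assumed number of independent variables, and the documents give none.

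**Conclusion.** The point holds as a recommended improvement, not as a defect in validity. The primary comparison is unadjusted, candidate maternal variables are collected, and the described randomisation balances none of them. Adjustment would change power from 80% to somewhere between about 79% and 91%, and the CI half-width from 7.0 to somewhere between about 7.1 and 5.9 mg/dL.

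These figures rest on the back-solved SD of 14.7 mg/dL, an assumed R² of 0 to 0.30, one covariate linearly related to the outcome, and complete data on 35 per arm. The documents do not say where R² lies, so a definite loss of precision should not be claimed.

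**What to change.** Fit a linear regression of first neonatal glucose on allocated arm plus one or two maternal covariates. Report the adjusted mean difference with its 95% CI alongside the planned unadjusted result.

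- **Covariates.** Name them in the SAP. They should be measured before allocation, already in the record, and chosen on clinical grounds. Last HbA1c or BMI would be examples if recorded; the documents do not confirm that either is. Do not use intrapartum or delivery variables, which arise after allocation, and do not select covariates by baseline P-values.
- **Status.** Make the adjusted model primary only if it is fixed before outcome data are seen. Otherwise keep the planned test as primary and label the adjusted model a sensitivity analysis.
- **Details to state.** Say how missing covariate values are handled, and what is done if glucose is clearly non-normal, since the model has no counterpart to the planned rank-sum route.

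The cost is a short SAP addition and one regression command in the software already named, with no new patients. It uses one or two degrees of freedom and loses under 1 point of power per covariate if the covariate is not prognostic. New data collection is avoided only if the chosen variables are in the record.
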